A. General Approach: We propose to understand the role of scES activating spinal circuits and weight-bearing stand training on the recovery of below injury voluntary control of movements, standing, and the autonomic nervous system function in humans with severe paralysis. Training will consist of lying supine or sitting while (1) practicing voluntary movements with specific Vol-scES configurations designed for the voluntary movements of the legs and trunks; or (2) maintaining normal systolic blood pressure during maneuvers of orthostatic stress with specific CV-scES configurations. By comparing among the two Group A interventions we will assess whether scES with specific configurations for each function are needed to improve

the ability to move voluntarily and/or recovery of cardiovascular function. Group B will have the same training but will also include weight-bearing stand training. Comparing across Group A and B, we will assess the role of stand rehabilitation for improving the ability to move voluntarily, and/or recovery of cardiovascular function. In a secondary study we will evaluate the effect of these 4 interventions of respiratory, bladder, bowel and sexual function in these individuals with chronic severe spinal cord injury. Quality of life and costs of health care also will be measured.

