b. Interventions. After recovery from surgery, *post-implant, pre-intervention* behavioral and cardiovascular assessments will be conducted (Appendix #1). Mapping of the motor evoked responses related to spatial electrode selection, amplitude and/or frequency [72] will be conducted and the specific configurations and parameters optimal for voluntary movement, standing and cardiovascular function will be identified. The pattern of electrically active electrodes, as well as electrode amplitude, stimulating frequency, and stimulating pulse width can be remotely programmed. Since different spatial activation patterns and frequency parameters affect different spinal circuits, the array can be reconfigured, within limits, to bias its facilitating effects toward different functional activities, such as standing or voluntary movement or physiological responses such as blood pressure regulation. After determining the configurations for voluntary, standing, and blood pressure regulation, the individual will then begin his or her assigned group intervention for approximately 80 sessions for 6 hours each session. After intervention #1 is completed, the *post-intervention #1* assessments will be conducted (Appendix #1, post-intervention #1) and the individual will continue to complete his or her second assigned group intervention. *Post-intervention #2* assessments will be conducted after the completion of the second intervention. After about 40 sessions in each intervention, mid-training assessments will be conducted.

4. Experimental Groups/Interventions (n=36 research participants).

Two factors are varied in this study, the stimulation frequency (voluntary, cardiovascular, or standing) and the presence or absence of weight bearing stand training. Crossing these yields 4 possible interventions: A1, A2, B1, and B2, where A=no weight bearing stand training, B=with weight bearing stand training, 1=voluntary parameters Vol-scES and 2=cardiovascular parameters CV-scES. A description of each of the four different interventions is provided below.

Group A:

- Vol-scES during voluntary leg movement training while sitting or lying supine (A1).
- CV-scES during sitting or lying supine (A2).

Group B:

- Stand-ES during stand training + Vol-scES during voluntary leg movement training (B1).
- Stand-ES during stand training + CV-ES during sitting or lying supine (B2).

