Hypothesis 1a: Primary Efficacy Hypothesis: CV-scES will result in greater cardiovascular functional improvements than those achieved during Usual Care Intervention.

Hypothesis 1b: Secondary Efficacy Hypothesis: Task specific voluntary movement training using Vol-scES will result in greater improvements in voluntary movement than those achieved during Usual Care Intervention.

Hypothesis 1c: Secondary Efficacy Hypothesis: Stand Stand-scES (parameters optimized for standing) will result in greater improvements in the ability to stand than those achieved during the Usual Care Intervention.

Secondary Analyses:

Hypothesis 1d: Task specific voluntary movement training using Vol-scES (parameters optimized for voluntary movement) will result in more successful voluntary movements than CV-scES.

Rationale: We propose that the spinal circuitry is the key integrator of complex signals from the periphery and supraspinal centers that drive the final motor pool output. We predict that the circuitry is continuously adapting to activity-dependent events that functionally configure the spinal networks to optimize generation of a specific motor task. Other possibilities are that the scES retrogradely stimulates residual axons that anatomically cross the lesion but are not functional, or, that scES restores the conduction properties that are lost with demyelination or other consequences of damage [2, 70, 73-76]. If only the restoration of the conduction of the residual supraspinal connections are needed, then the scES **alone** without voluntary training should be sufficient to restore voluntary movement of the legs. However, if the spinal cord circuitry is a key controller, then task specific training of voluntary movement in the presence of scES would also be required to optimally generate voluntary movement.

Methods: Linear statistical models will be fit with coefficients relating to the three stimulation methods. This hypothesis will be tested by if the Vol-scES estimates are significantly higher than those for CV-scES or Stand-scES stimulation parameters. See Section G for details.

Hypothesis 1e: CV-scES (parameters optimized for cardiovascular function) will result in greater cardiovascular functional improvements than Vol-scES.

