Procedure: Participants will participate in laboratory sessions until all optimal configurations for joint movement and trunk control are found. Participant will demonstrate safe use of the patient programmer and ability to perform the leg voluntary movement independently or in the presence of a care giver. This will take approximately 3–5 days. Once the participant has demonstrated safe use of programs they will be allowed to conduct the sessions at home. Participants will be asked to train daily (7 days a week) for a total of 80 sessions.

Participants in the Voluntary-scES group (A1) will receive Core voluntary training focusing on trunk exercises, sitting balance, and lower extremity training for 6 hours daily. Voluntary training will be performed in the laboratory under supervision of trained research staff until they can perform each task safely and independently. Then they will be able to conduct their training at home. Approximately every two weeks, lower extremity voluntary configurations will be assessed by research staff to make sure they are still optimized for the desired movement. They may train in the laboratory more often.

3. Cardiovascular Intervention.

Participants will undergo testing in the laboratory to determine the optimal stimulator configuration(s) for blood pressure regulation. The first 5 training sessions will be performed in the laboratory. Once 3 consecutive stable days are achieved with the same stimulation parameters and the participant has demonstrated safe use

of the programmer, they will be sent home for one day to perform the stimulation at home. The participant will return to the laboratory the following day for stimulation with blood pressure monitoring. Provided cardiovascular parameters remain stable, the participant will be allowed to train at home for 3 days prior to returning to the laboratory for stimulation with monitoring. If cardiovascular parameters remain stable, the participant will be able to begin the home training program of 6 days a week and 1 day in lab training. Participants will be asked to train with CV-scES for CV for approximately 6 hours daily (7 days a week) for a total of 80 CV training sessions. Participants are instructed to monitor blood pressure for at least 15 minutes prior to starting CV-scES each day in order to insure a stable baseline prior to starting stimulation.

4. Stand Intervention.

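### A1 versus A2 compares whole regimens, so it cannot show whether function-specific stimulation configurations are needed: voluntary practice always accompanies Vol-scES and never CV-scES

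*Protocol*

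**What the plan says.** The General Approach (III.A) sets out the inference: "By comparing among the two Group A interventions we will assess whether scES with specific configurations for each function are needed to improve". The outcomes it names are voluntary movement and cardiovascular recovery, either or both.

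Section III.B.4 describes the design as two-factor: "Two factors are varied in this study, the stimulation frequency (voluntary, cardiovascular, or standing) and the presence or absence of weight bearing stand training". Voluntary-movement training is not named as a factor. The same section defines the four arms:

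- A1: "Vol-scES during voluntary leg movement training while sitting or lying supine (A1")
- A2: "CV-scES during sitting or lying supine (A2")
- B1: "Stand-ES during stand training + Vol-scES during voluntary leg movement training (B1")
- B2: "Stand-ES during stand training + CV-ES during sitting or lying supine (B2")

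Section III.E.2 says that A1 participants "will receive Core voluntary training focusing on trunk exercises, sitting balance, and lower extremity training for 6 hours daily". Section III.E.3 gives the CV intervention about the same daily stimulation time and describes no voluntary practice. The opening summary and III.A link CV-scES to maneuvers of orthostatic stress.

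In III.B.4 the second period moves A1 to B1 and A2 to B2, while B1 and B2 repeat. The Methods under hypotheses 1d and 1e (III.C) test whether estimates for one set of stimulation parameters exceed those for the others. The linear model in Section G has terms for stimulation setting and for stand training within setting, and none for voluntary practice.

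**The concern.** Each configuration comes with its own task. A difference between A1 and A2 can therefore arise from the electrode configuration, from the task practised under it, or from both. The protocol says it will read the difference as evidence about configuration.

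What is at stake is the stated configuration-specificity conclusion and its two secondary hypotheses. A positive 1d would be reported as an effect of stimulation parameters when daily practice of the measured skill could explain it. For 1e the comparison also mixes configuration with task, and neither the share due to configuration nor the direction of the net bias is known.

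**Working it through.** **Arms side by side** (III.B.4 with Table 1; III.E.2; III.E.3)

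| Arm | n | Configuration | Voluntary practice | Stand training, period 1 | Stand training, period 2 |
|---|---|---|---|---|---|
| A1 | 9 | Vol | yes | no | yes |
| A2 | 9 | CV | no | no | yes |
| B1 | 9 | Vol | yes | yes | yes |
| B2 | 9 | CV | no | yes | yes |

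The configuration and practice columns coincide: 9 + 9 = 18 of 18 Vol participants practise and 0 of 18 CV participants do. No arm in either period has Vol-scES without practice, or practice under CV-scES.

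**Planned exposure.** 6 h × 80 sessions = 480 h of training in a period, and 480 × 2 = 960 h over both. These are nominal hours from the schedule and do not measure bias. The CV arms are not literally at zero, because Appendix 1 schedules voluntary-movement and torque assessments through the intervention without restricting them by arm.

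**What the contrast estimates.** Let c_Vol and c_CV be the configuration effects, p the effect of voluntary practice and q the effect of the task tied to CV-scES. In the Section G model, β_Vol absorbs c_Vol + p and β_CV absorbs c_CV + q. So

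β_Vol − β_CV = (c_Vol − c_CV) + (p − q).

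The contrast with stand training adds β_VT − β_CVT and leaves (p − q) in place.

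**Rank check.** The Vol and CV part of the model (β_Vol, β_CV, β_VT, β_CVT) has 4 columns and rank 4. With an indicator for voluntary practice it has 5 columns and still rank 4, in period 1 and in both periods together. The correlation between the Vol-scES and practice indicators is 1.0. Adding a hypothetical cell with CV-scES and voluntary practice raises the rank to 5, so the missing cell is the cause.

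**The plan's own figure.** Section G gives 90% power for an effect size of 1.7 with one-sided α of 0.05. Under the normal approximation, power = Φ(1.7/√(2/n) − 1.645).

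- n = 6 per group (III.B): Φ(2.944 − 1.645) = 90.3%, which reproduces the stated figure. The exact t gives 86.3%.
- n = 9 per group (Table 1): Φ(3.606 − 1.645) = 97.5%. The exact t gives 96.4%.

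This power is for detecting the sum above and says nothing about its parts.

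**Illustration with assumed effects.** Suppose configuration has no effect (c_Vol = c_CV), q = 0, and practice alone shifts a voluntary-movement outcome by p standard deviations. With 9 per arm, 16 degrees of freedom and noncentrality p/√(1/9 + 1/9), the one-sided A1 versus A2 test rejects in:

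| p (SD) | Probability of rejection |
|---|---|
| 0 | 5.0% |
| 0.5 | 26.5% |
| 1.0 | 65.0% |
| 1.7 | 96.4% |

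The documents give no practice effect, so these rows show a range and are not a forecast.

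**The case against.** The strongest reply is that hypothesis 1d is already worded as a regimen comparison: task-specific training using Vol-scES against CV-scES. III.A also describes the two Group A programmes, each with its task, just before it draws the inference. This stands. The hypothesis as worded can be tested. What fails is the conclusion in III.A, the two-factor description in III.B.4 and the stimulation-parameter reading in the Methods.

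Several stronger readings are tempting, and the documents do not support them.

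- **That 1e sets a practised group against a resting one, so that practice could produce a positive result.** A2 is not simply resting, since III.A ties orthostatic-stress maneuvers to CV-scES. The Rationale on cardiac structure and function (II.B.2.b) suggests that scES set for voluntary or stand training may activate leg muscle and improve venous return. On that account, activity in A1 could narrow any CV-scES advantage and so work against 1e. The configuration effect in 1e is unidentified, but its bias should not be assumed to resemble that in 1d.
- **That the 1d rationale promises to separate scES alone from scES with training.** It gives conditional predictions: if restored conduction is all that is needed, scES alone "without voluntary training should be sufficient to restore voluntary movement of the legs"; if the spinal circuitry is a key controller, training would also be required. It does not say that this trial will separate the two.
- **That the main efficacy claims are compromised.** 1d and 1e are listed as secondary analyses. Hypotheses 1a to 1c are tested against baseline by paired t-tests and do not use A1 versus A2.
- **That the assessments with and without stimulation rescue the comparison.** They measure an acute effect at a visit and cannot separate the configuration used over 80 sessions from the task practised under it.

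**Conclusion.** The point holds as a wrong stated inference. Configuration and task are completely aliased across both periods, so A1 versus A2, and likewise B1 versus B2, compare regimens. For 1d the share of any difference due to configuration is unidentified, and practice could account for all of it. For 1e the configuration effect is also unidentified. Voluntary practice may bias against 1e, while the maneuvers tied to CV-scES could act the other way.

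This rests on the arm definitions as written, in particular that A2 and B2 receive no programme of voluntary training. It does not depend on sample size or on any choice left to an analysis plan, because no analysis of these four arms can supply the missing cell. The rejection rates above do rest on assumed effects. The regimen comparison itself remains valid and useful.

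**What to change.** State in III.A, in III.B.4 and in the Methods of hypotheses 1d and 1e that these comparisons are between regimens: Vol-scES with voluntary training against CV-scES without it. Amend the two-factor sentence to say that the task differs with the configuration. Delete the claim that A1 versus A2 shows whether a specific configuration is needed. The cost is protocol wording and a narrower claim for two secondary hypotheses.

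Optionally, report the stimulation on/off difference at the Post-Implant/Pre-Intervention visit for the FNPA, the torque assessment and the neuromuscular voluntary movement assessments. Appendix 1 already marks these as done with and without stimulation, so this is one added within-participant comparison on scheduled data. It tests the acute effect of scES before the training programme, apart from brief exposure while configurations are being found. The text should state two limits:

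- it does not estimate the effect of prolonged scES without practice;
- on/off results after the interventions do not isolate training from cumulative stimulation.

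Separating configuration from practice would need a further cell, such as CV-scES with voluntary training. That is not required if the claim is narrowed.

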b. Pre-Screening (1st consent). If the potential research participant agrees to screening we will give them the choice to conduct some pre-screening assessments at their location. Pre-screening will be offered because the majority of the research participants will likely not be from our geographic region. Travel and housing costs will be the research participant's financial responsibility. Therefore, we would like to allow a pre-screening process to avoid those who would be ineligible after review of standard medical assessments having to travel to Louisville at their expense. They will also have the option to have all the pre-screening assessments conducted at the Kentucky Spinal Cord Injury Research Center in Louisville.

If they choose the pre-screening option, the clinical coordinator will request their medical history related to their spinal cord injury that may include surgical and medical records from their initial injury; spinal cord MRIs, DXAs, hospitalizations and/or surgeries they have had since their injury; and medical records from their physician visits that document their overall health. We will also have them fill out a self-report of their medical status. If they have not had a spinal cord MRI within 3 years, we may request they obtain one. We will request a drug screening test. If they are female, they will be asked to obtain a pregnancy test. All medical tests will be covered by the research study using a pre-paid credit card loaded with the costs of the tests. The clinical coordinator will obtain pricing and send a gift card pre-loaded with the funds for the testing to avoid any insurance billing or out of pocket expense. The clinical coordinator will work with the potential research participant to identify the medical location for the tests and the costs and will provide the pre-paid credit card for payment. The individual can decide if they would like to conduct all or some of these medical tests at their location.

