The EQ-5D-3L captures an individual's self-reported health status at the time they complete the questionnaire. The EQ-5D-3L consists of 2 pages – the EQ-5D descriptive system and the EQ visual analogue scale (EQ-VAS). The EQ-5D-3L descriptive system comprises the following 5 dimensions: mobility, self-care, usual activities, pain/discomfort and anxiety/depression. Each dimension has 3 levels: no problems, some problems, extreme problems. The respondent is asked to indicate his/her health by ticking (or placing a cross) in the box against the most appropriate statement in each of the 5 dimensions. The EQ VAS records the respondent's self-related health on a vertical, visual analogue scale where the endpoints are labeled 'Best imaginable health state' and 'Worst imaginable health state.' This information can be used as a quantitative measure of health outcome as judged by the individual respondents [96]. Furthermore, we will conduct qualitative interviews.

Methods: In this study, we will employ SCI-FI scales to examine intervention impacts on the following quality of life domains: Basic mobility, Self-care, Fine Motor Function, Wheel Chair Mobility, and Ambulation. The SCI-QOL measures include: Bladder Management, Bowel Management, Pain Interference, Depression, Anxiety, Resilience and Ability to Participate in Social Roles/Activities. We will also administer the PROMIS global satisfaction with sexual function along with the Pure Pain Scale and the Revised Life Events Survey. We may assess these pre-usual care, post-interventions and during follow-ups.

Additionally, we will employ the EQ-5D-3L scales to examine the intervention impacts on the following quality of life domains: mobility, self-care, usual activities (e.g. work, study, housework, family or leisure activities), pain/discomfort, and anxiety/depression. Finally, we will conduct qualitative interviews using an interview guide developed specifically for this study that has been pilot tested.

Specific Aim 5.

Measure impact of scES and training on healthcare resource utilization.

Secondary Analyses:

Hypothesis 5a: Healthcare resource utilization will decrease with scES.

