Rationale: SCI injuries are often accompanied by respiratory, cardiovascular, bladder, bowel and sexual dysfunction requiring greater healthcare utilization. The economic impact on the increased use of healthcare can be devastating. It is estimated that the total cost of care in the years after the first year of injury is \$165,554. The total cost of care includes the cost of hospitalization each year, nursing home care, outpatient services, physician fees, equipment, environmental modifications, supplies, attendant care, and vocational services [97].

Methods: We will collect healthcare resource utilization information from each research participant's insurance provider from two years prior to the intervention to two years after the intervention. We will also enroll a control group to more precisely estimate changes in resource utilization. The control group will be selected from the Neurorecovery Network (NRN) and will be enrolled under a separate protocol. Patients with complete or incomplete cervical or thoracic SCI are referred to the NRN and there receive intense locomotor training for three to four months. Controls will be matched on age, level of severity, duration of injury, and insurance type. Resource utilization data will be assigned to one of the cost categories above and a cost estimate will be assigned to the resources.

D. Outcomes

1. Functional Movement Assessments (Voluntary movement of legs and trunk)

a. Multi-Segmental Motor Responses (MMR)

Procedure: Motor responses in different leg muscles can be evoked by non-invasive stimulation of the dorsal lumbosacral spinal cord and recorded [98-100]. Such Multisegmental Monosynaptic Reflexes (MMR) [101, 102] are the basic components of the lower-limb muscle responses that are elicited by epidural stimulation of posterior lumbar cord structures. MMRs will be evoked by stimulating the spinal cord percutaneously between the T9 and L4 spinous processes. The AgCl cathode (pre-gelled, soft surface electrode) will be placed over the skin between T9 and T10, T10 and T11, T11 and T12, T12 and L1, L1 and L2, L2 and L3, and L3 and L4 spinous processes and two 50 x 100 mm large anodes will be placed bilaterally over the anterior spine of the iliac crest. The optimum site of stimulation will first be located by a hand-held electrode. The site of stimulation will be selected based on where the motor responses can be elicited in all the recorded muscles as

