A medical event is defined within our program as “any untoward or unfavorable medical occurrence in a human research participant that occurs during the same time period the research participant is enrolled in the study and is not study related and is not serious.” It is an anticipated medical issue that is unfortunately common to individuals with chronic spinal cord injury and can occur daily, weekly monthly, or several times a year. These medical events can include urinary tract infections, kidney stones, hypotension, autonomic dysreflexia, skin sores and pressure sores with prolonged healing, joint swelling, joint soreness, joint sprain, ligament sprain, fracture, infections (non-UTI), spasticity and falls. Our standard operating procedure is that if any of these medical issues arise while directly participating in our research, if not immediately resolved, the study physician is notified and the individual is referred to the appropriate medical care. This medical care can be provided by our study physician or their colleagues or by the medical specialist of the research participant’s choice. The study physician can medically treat the issue to resolution, if appropriate, and the research participant chooses the study physician as their clinical choice for medical treatment. In this case the study physician would notify the principal investigator only if the medical issue affects their medical eligibility in the study or any of the research assessments or training paradigms. If another physician treats the medical issue the study physician will follow the individual to only assess whether the medical condition affects their medical eligibility in the study or any of the research assessments or training paradigms and will notify the principal investigator. All non-study related medical events are followed by the research team and will be reported to the IRB at the time of the continuing annual review. A weekly report of all medical events is generated by the research nurse and sent to the study physician (and physician assistant), the principal investigator, and the study physical therapists.

E. Data and Safety Monitoring Board

[name], PhD (Chair of DSMB)

Neurosurgeon, Clinical Professor

Department of Neurological Surgery

University of Miami and The Miami Project to Cure Paralysis, Miami, FL

[name]

Cardiologist, Professor of Medicine

Johns Hopkins Hospital, Baltimore, MD

[name], PhD

Urologist

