Appendix #1

Appendix 1. Frequency of Outcomes for Aims 1 – 3.

Assessment Category #=with and without stim	Assessments	Pre-screen	Screen	Pre-Usual Care	Pre-implant	Post-Implant/ Pre-Intervention	Weekly	Periodic Through Intervention	Monthly	Post-Intervention #1	Post-Intervention #2	Follow Up(s)
Medical	SC MRI	X	or X									
	ASIA		X	X	X					X	X	
	Physician and PT Medical		X	X	X					X	X	X
	Pregnancy	X	X									
	Blood Work		X	X	X					X	X	X
	Drug Testing	X	X	X	X	X	X	X		X	X	X
Voluntary	MMR		X									
	FNPA		X	X	X	X#				X#	X#	X#
	NRS trunk and leg score		X	X		X#		X#		X#	X#	X#
	Lower Extremity Torque with EMG					X#		X#		X#	X#	X#
	Neuromuscular Voluntary Movement Assessments					X#		X#		X#	X#	X#
Cardiovascular	Ambulatory BP monitoring		X	X				X	X	X	X	X
	Ambulatory HR monitoring		X	X				X	X	X	X	X
	12 lead ECG				X					X	X	
	Orthostatic Stress Test		X	X	X	X#		X#		X#	X#	X#
	Vascular Ultrasound			X	X	X#		X#		X#	X#	X#
	Echo-cardiography		X	X	X	X#		X#		X#	X#	X#
	Arterial pulse wave velocity		X	X	X	X#		X#		X#	X#	X#
	Sympathetic skin responses				X					X	X	
Stand	Dexa		X		X					X	X	X
	Independence levels during stand -			X	X	X#	X#	X#		X#	X#	X#
	Standing Assessments				X	X#		X#		X#	X#	X#
Respiratory	Pulmonary Function Test		X		X	X#				X#	X#	X#
	Respiratory Motor Control Assessment		X		X	X#				X#	X#	X#
	Resting metabolic rate		X	X	X					X	X	X

Assessment Category #=with and without stim	Assessments	Pre-screen	Screen	Pre-Usual Care	Pre-implant	Post-Implant/ Pre-Intervention	Weekly	Periodic Throughout Intervention	Monthly	Post-Intervention #1	Post-Intervention #2	Follow Up(s)
Bladder	Urodynamics		X	X	X					X	X	X
	Bladder Questionnaire			X	X					X	X	X
	Urinalysis			X	X					X	X	X
	Ultrasound			X	X					X	X	X
Bowel	Bowel Questionnaire			X	X					X	X	X
	Anorectal Manometry			X	X					X	X	X
Sexual Function	International Dataset (Males)			X	X					X	X	X
	International Dataset (Females)			X	X					X	X	X
Quality of Life	SCI-QOL		X		X					X	X	X
	SCI-FI		X		X					X	X	X
	PROMIS		X		X					X	X	X
	EQ-5D-3L		X		X					X	X	X

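### Aim 5 takes utilisation from insurer records alone, with no rule for clinical care the study delivers or pays for, so a fall could not be told apart from a change of payer

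*Protocol*

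**What the plan says.** Protocol section III.C, Specific Aim 5, states a directional hypothesis: "Hypothesis 5a: Healthcare resource utilization will decrease with scES". Its Methods name the source, "We will collect healthcare resource utilization information from each research participant's insurance provider", and the period, "from two years prior to the intervention to two years after the intervention". The resources are then sorted into cost categories and given a cost. Controls come from the Neurorecovery Network under a separate protocol, matched on age, severity, duration of injury and insurance type. No second source is named for participants, and nothing says how care supplied by the study is counted. Section III.H lists lower health care costs among the things whose efficacy the trial is to establish.

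Elsewhere the Protocol describes care that the study supplies or may supply:

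- III.B.3.a: implant surgery, an overnight hospital stay, nurse follow-up at home, and medical care for complications.
- IV.C.2.a: immediate medical care during assessments and training when needed.
- IV.D, on medical events: "This medical care can be provided by our study physician or their colleagues or by the medical specialist" that the participant chooses. It adds "The study physician can medically treat the issue to resolution, if appropriate", on condition that the participant picks that physician.
- III.B.1.b: pre-screening tests paid by the study, for which the coordinator is to "send a gift card pre-loaded with the funds for the testing to avoid any insurance billing or out of pocket expense".

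**The concern.** An insurer's file shows what was billed to that insurer. If part of a participant's clinical care moves to the study's account during or after the intervention, the file shows less care although the participant received just as much. Hypothesis 5a would then be supported by a change of payer.

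The setting makes some movement plausible. Participants must live in Louisville during the study, and the Protocol expects most of them to come from outside the region (III.B.1.a and b). They are therefore away from their usual providers for two periods of at least 80 sessions, in daily contact with a team that includes physicians. Most of the two years before the intervention lies outside that arrangement.

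The cost claim has a second exposure. If the study pays for the implant, hospital night, device, washout or explant, none of these enters an insurer-only cost result. Section IV.B puts infection with washout in its 11-30% band.

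**Working it through.** **Figure to reproduce.** None. The Protocol gives no effect size, sample size or power for Aim 5.

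**Which care falls where, and who pays**

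| Care | Protocol section | Timing | Payer stated? |
|---|---|---|---|
| Pre-screening tests (possible MRI, drug screen, pregnancy test) | III.B.1.b | before Usual Care and implant | yes: the study |
| Implant, hospital night, complications | III.B.3.a | between Usual Care and training, and later | not in the text shown |
| Immediate care at sessions | IV.C.2.a | mainly during intervention | not in the text shown |
| Treatment by the study physician | IV.D | while enrolled, at the participant's choice | not in the text shown |

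The only care with a stated payer lies on the before side.

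**Direction.** Let true utilisation be the same before and after. Let f_pre and f_post be the shares of otherwise billable care that are off insurance. Then

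apparent change = (1 − f_post)/(1 − f_pre) − 1.

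The documents give neither share. The range below is an assumption (0-10% before, 0-20% after).

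| f_pre \ f_post | 0% | 2% | 5% | 10% | 20% |
|---|---|---|---|---|---|
| 0% | 0 | −2.0% | −5.0% | −10.0% | −20.0% |
| 2% | +2.0% | 0 | −3.1% | −8.2% | −18.4% |
| 5% | +5.3% | +3.2% | 0 | −5.3% | −15.8% |
| 10% | +11.1% | +8.9% | +5.6% | 0 | −11.1% |

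Example: f_pre = 5% and f_post = 10% give 0.90/0.95 − 1 = −5.3%. A spurious fall needs f_post > f_pre; the reverse gives a spurious rise. For scale only, 5% of the Protocol's reference cost of $165,554 is 0.05 × 165,554 = $8,278.

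**Controls.** The bias left after comparison is the participants' apparent change minus the controls'. With participants at f_pre = 0, f_post = 10% and controls at 0 and 0, it is −10% − 0 = −10 percentage points. If the controls also moved to 10%, it is zero. Matching on age, severity, duration and insurance type does not equalise these shares. Controls receive a different programme, and how their care is billed is not stated.

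**Scheduled assessments.** In Appendix 1, "Physician and PT Medical", blood work and urodynamics are each marked at three time points before the intervention (Screen, Pre-Usual Care, Pre-implant). From Post-Intervention #1 onward there are four (two post-intervention points plus follow-ups at 6 months and 1 year). Ultrasound has two and four. They fall on both sides and are research assessments, so they show no one-sided displacement and belong in neither window.

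**The case against.** The strongest reply is that no displacement after the intervention is shown. Section IV.D reads like ordinary clinical referral: the study physician is one option among several, and the care may well be billed to insurance. Consent pages, where payment terms often stand, are not in the text, so silence on the payer is no fault of the plan. The second year after the intervention has no scheduled study contact. Study assessments may also generate billed care, since section III.D.5.d notes that abnormal ultrasound findings may need further diagnosis. All of this stands, and it leaves the net direction open.

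A reader might infer from the gift-card arrangement that the study keeps participants' care off insurance in general and so manufactures a fall. The documents do not support that. The arrangement covers eligibility tests before the intervention; if they replaced billed care at all, they would lower the before count and work against a fall. Nor does the Protocol say that study physicians routinely treat events themselves.

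It can also be said that costing perspective belongs in an analysis plan, and that leaving the implant out of downstream utilisation is a legitimate perspective. Both are fair as to costing. The data source is different: the Protocol fixes it, and an analysis plan cannot count care that nobody set out to collect.

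**Conclusion.** The point holds in a limited form. Insurer records are the only utilisation source named for a directional hypothesis, and the Protocol has no rule for clinical care that the study delivers or pays for. A spurious fall is possible but not demonstrated. Its size equals the post-intervention share moved off insurance when nothing is moved before, and is zero when the shares are equal. The percentages rest wholly on assumed shares. The planned controls would not clearly remove the bias, though that depends partly on a separate protocol not at hand. Aim 5 is secondary, so the trial's primary conclusion is untouched. The change is still worth making: as the plan stands, a fall in insurer-recorded use could not be separated from a change of payer.

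**What to change.** In the Aim 5 Methods:

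1. Define utilisation as clinical care regardless of payer. Add to the insurer records any clinical care delivered or paid for by the study, at the same unit costs, and match items so that billed care is not counted twice.
2. Take the additional items from the medical-event log, the research medical record and, for implant complications, the Adverse Event Forms.
3. Apply the same rule to the controls as far as their separate protocol allows, and state any remaining difference.
4. Exclude research-only assessments, including pre-screening tests, from both windows.
5. Report the cost result with and without the implant and its complications.

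The cost is modest. The log, weekly report and research record are already kept (IV.D, IV.C.1, Appendix 2), so the work is abstraction and a paragraph of text. The downside is that the cost result may look less favourable. If all clinical care was in fact billed to insurers, the utilisation total does not change.
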